For PWD at Experimental Sites, at the beginning of the Intervention Period, PEER groups will be formed. Each group will consist of one Resident-Leader (RL) and five Resident-Players (RPs). Each RL will serve as a facilitator for a consistent group of RPs. There will be two groups per Experimental site. PWD will be invited to participate in PEER sessions twice per week for 4.5 months (36 total sessions); each PEER session is expected last about 45 minutes. If PWD or staff are unable to attend (e.g., due to illness or a doctor's appointment), researchers will simply note their absence. MPES data will be collected during PEER sessions, as well as Treatment Fidelity / Process measures—i.e., Session Observation / Evaluation Forms (described below). Observations of the PEER groups will be conducted in person or via web stream as an infection control protocol, to limit exposure of participants to additional staff. For RLs, we will track the extent to which he/she follows each of the key steps required for successfully implementing each activity and the degree of staff assistance required.

For PWD at Experimental Sites, PWD will participate in standard care for 4.5 months.

SPs

SPs' participation will begin by attending an in-person training on PEER. Prior to and after the training, SPs will take a quiz (to examine knowledge transfer). In addition, satisfaction questions will be posed to staff after taking the training.

In addition, researchers will implement two PEER sessions with residents while site staff observe and assist, so site staff will become familiar with the app in a real-life setting.

The knowledge and experience that staff gain from the training will prepare them to properly implement the PEER intervention. To help remind staff members of the key aspects of the training, two quick-reference sheets will also be available in the app to staff at the completion of the training modules: one quick reference sheet for the "Setting Up PEER Activity Session" and one quick reference sheet for "10 Tips for 'Training' a Resident to Lead PEER Activities." These quick reference sheets (each of which will be one page) will include key information from the training, stated as succinctly and clearly as possible.

We have purposefully decided not to use a long and detailed implementation manual for two main reasons. First, the PEER app will guide the staff member and Resident Leader through each activity step by step, so an implementation manual is essentially be embedded within the app. Second, in past studies, we had given staff members extensive implementation manuals, but the manuals were typically ignored by staff. This is not surprising, since staff are very busy with main caregiving and other responsibilities. If they need to refer to a long reference manual, it would be nearly impossible for them to have time to implement an intervention. In addition, some staff have low literacy (especially caregivers) and/or speak English as a second language. For such staff, it may be difficult to comprehend and remember all of the information included in such a detailed manual.

As such, we have found that the best way to ensure staff properly follow an intervention such as the PEER app is to (a) embed the steps required to implement the intervention into the app itself, (b) provide high-quality, interactive, training on how to use the intervention, (c) provide an opportunity for staff to observe researchers implementing PEER with residents, and (d) provide quick reference sheets (in this case, one quick reference sheet for each of the two training modules).

After taking the PEER training and observing researchers facilitating at least two PEER sessions, staff will then enter the Intervention Period. Staff will be invited to participate in PEER sessions twice per week for 4.5 months; each PEER session is expected last about 45 minutes. Activity staff will oversee programming. Other staff (CNAs, managers, etc.) will observe programming so feedback can be elicited. Each activity type will be used at least six times by each PEER group. Satisfaction questions will be posed to SPs at the end of each PEER session. After the Intervention Period has ended, SPs will also be posed final satisfaction questions.

8.0 STUDY MEASUREMENTS AND PROCEDURES

All measures are included in the Appendix

PWD

Baseline Assessments / Observations

1. Chart Review Form

- a. A researcher will conduct a CHART REVIEW to collect the following data:
 - i. Demographics (race/ethnicity, education level, marital status, and number of years living in LTC)
 - ii. All diagnoses
 - iii. Type of dementia
 - iv. All meds

2. Mini Mental Status Exam (MMSE)

A researcher will conduct a direct interview with the PWD to complete the MMSE.

- a. The MMSE is a structured evaluation aimed at evaluating aspects of cognition in elderly residents. The MMSE assesses patient attention, level of orientation, and ability to recall information. These are the sections of the MMSE assessment:
 - i. **Orientation to Time:** temporal orientation is evaluated by asking the resident to recall temporary coordinates (current year, season, month, day of the week, and date). These are to be asked in separate questions and about 30 seconds are to be given for response. [TOTAL POSSIBLE POINTS: 5]
 - ii. **Orientation to Place:** the resident is asked details of their current location (name of the state, county, city, building, and floor of the building). These are to be asked in separate questions and about 30 seconds are to be given for response. [TOTAL POSSIBLE POINTS: 5]
 - iii. **Registration:** the resident is asked to repeat three words that are to be given by the assessor. The accuracy of their word reproduction is assessed. Also, the resident is informed that they will need to remember the words at a later moment during the evaluation. [TOTAL POSSIBLE POINTS: 3]
 - iv. **Attention and Calculation:** the resident is asked to subtract 7 from 100, and then continue to subtract 7 from each answer (in a series of 5: 93–86–79–72–65). The accuracy of their calculations is assessed. If the resident refuses to perform the series of calculations, the assessor will ask the resident to spell the word “WORLD” forward, then backward. Only the accuracy of the backward-spelling (per-letter) is assessed. [TOTAL POSSIBLE POINTS: 5]
 - v. **Recall:** the resident is asked to recall the three words given in the *Registration* stage of the assessment. The accuracy of their recollection of all three words is assessed. [TOTAL POSSIBLE POINTS: 3]
 - vi. **Naming:** the resident is asked to name two separate items that the assessor points to, typically starting with the assessor’s writing implement (assessor points to pencil or pen). The second item is typically a wristwatch, but this can be substituted if the assessor isn’t wearing a common wristwatch. Substituted items must be visually recognizable/familiar, such as a pair of eyeglasses, a standard key (to a door), or a simple water bottle. The accuracy of the terms/names given to both items by the resident is assessed. [TOTAL POSSIBLE POINTS: 2]
 - vii. **Repetition:** the resident is asked to repeat an entire phrase to be stated by the assessor (“No ifs, ands, or buts.”) The accuracy of the resident’s reproduction of the phrase is assessed, with one point given only if each word (including pluralization) in the phrase is repeated correctly. [TOTAL

POSSIBLE POINTS: 1]

viii. **Comprehension:** the resident is asked to carry out three short tasks within a one-sentence instruction: “Take this paper in your right hand, fold it in half, and put it on the table (*or* hand it back to me).” The assessor pauses briefly between each task when giving the instruction before handing the resident a blank piece of paper. The assessor does not repeat instructions once the resident begins the tasks. The resident’s ability to accurately recall and perform each of the three tasks is assessed. [TOTAL POSSIBLE POINTS: 3]

ix. **Reading:** the assessor holds up a piece of paper with the words “CLOSE YOUR EYES” largely typed in the center and asks the resident to “Please read this and do what it says.” The resident can read the words aloud or to themselves, but the point is only given if the resident successfully completes the instructed task by closing their eyes. [TOTAL POSSIBLE POINTS: 1]

x. **Writing:** the resident is provided a pen or pencil and asked to write a sentence on a blank piece of paper (the same/unfolded blank paper used in the *Comprehension* stage of the assessment) provided by the assessor. If the resident is confused or overwhelmed with the broad instruction, the assessor rephrases the instruction with more specificity: “Write a sentence about the weather.” Errors in spelling or grammar are ignored, but a point is given only if the resident’s written sentence is comprehensible and contains a subject and a verb. [TOTAL POSSIBLE POINTS: 1]

xi. **Drawing:** the resident (still provided with a pen or pencil) is provided with a paper showing two intersecting pentagons and asked to reproduce/copy the design anywhere on the page’s available space remaining. A point is given based on the geometric accuracy of the design (if the resident’s drawing consists of two 5-sided figures that intersect to form a 4-sided figure). [TOTAL POSSIBLE POINTS: 1]

b. Each stage of the MMSE consists of one to five separately scored items, with each item awarded 1 or 0 points, and a total of 30 items. The higher the score, the lower the impairment to the cognitive response. Scores closer to 0 indicate severe cognitive impact whilst scores closer to 30 indicate an intact cognitive response.

i. Score Interpretation

0 - 9	Severe cognitive impact
10 - 16	Moderate impairment
17 - 30	Intact cognitive response

3. I'm Still Here Skills Inventory – PEER Version (ISH-SI-PV)

a. Please note: the ISH-SI-PV is only administered if the PWD scores below 5 on the MMSE)

b. This assessment asks the participant to read / respond to three pages of information.

i. On the first page, the PWD is asked to read the following aloud: “Today we take the telephone for granted. We can pick up the phone and call anywhere in the world. This would have seemed like magic to people who lived before 1876.”

1. Scoring:

0 - Unable to Read Aloud

- 1 - Able to Read 1 – 3 words aloud (out of 31)
 2 - Able to Read 4 – 25 words aloud (out of 31)
 3 - Able to Read 26 – 31 words aloud (out of 1)
- ii. On the second page, there is a photo of an old telephone, along with the following text, which the PWD is asked to read aloud: “This is an early phone from Sweden. Do you think it would be easy to use?”
 - 1. Scoring:
 - a. **Reading Ability**
 - 0 - Unable to Read Aloud
 - 1 - Able to Read 1 – 3 words aloud (out of 16)
 - 2 - Able to Read 4 – 11 words aloud (out of 16)
 - 3 - Able to Read 12 – 16 words aloud (out of 16)
 - b. **Ability to Answer Question**
 - 0 - No Response
 - 1 - Unintelligible Response
 - 2 - Simple Response (e.g., “yes” or “no” or “not sure” or “hard to say”)
 - 3 - Response with additional details (e.g., “No. I would have no idea how to use it...”)
 - iii. On the final page, there is the question “Do you like this food?” along with a photo of Brussel sprouts (with a caption beneath it that reads “Brussel Sprouts”) and buttons that say YES and NO.
 - 1. Scoring:
 - a. **Reading Ability**
 - 0 - Unable to Read Aloud
 - 1 - Able to Read 1 – 2 words aloud (out of 5)
 - 2 - Able to Read 3 - 5 words aloud (out of 5)
 - b. **Ability to Answer Question**
 - 0 - No Response
 - 1 - Unintelligible Response
 - 2 - Simple Response (e.g., “yes” or “no” or “not sure” or “hard to say”)
 - 3 - Response with additional details (e.g., “No. That looks gross!”)
 - iv. **All items are added together to calculate the Total Score**
 - 1. The score can be interpreted as follows:
 - 0 = INAPPROPRIATE for PEER Activities (ineligible)
 - 1 – 3 = POTENTIALLY appropriate for PEER Activities (eligible)
 - 4 – 10 = LIKELY to be appropriate for PEER Activities (eligible)
 - 11 – 14 = DEFINITELY appropriate for PEER activities (eligible)
- 4. **Dementia Quality of Life (DEMQOL)**
 - a. A researcher will conduct a direct interview with the PWD to complete the DEMQOL. However, if the PWD is unable to respond to questions on the DEMQOL, this measure will be collected via proxy interview (with a staff member who is familiar with the PWD).
 - b. The DEMQOL is a 28-item self-reported measure related to health-related quality-

of-life (HRQL) in residents with dementia. The DEMQOL takes cognition, negative emotion, positive emotion, social relationships, and loneliness into consideration. The DEMQOL-Proxy is a 31-item measure completed by the staff/caregiver and focuses on cognition, negative emotion, positive emotion, daily activities, and appearance.

- i. Each item on the DEMQOL (and DEMQOL-Proxy) has four response-options:
 - Not at all
 - A Little
 - Quite a Bit
 - A Lot
- ii. Most items are scored as follows
 - Not at all = 4
 - A Little = 3
 - Quite a Bit = 2
 - A Lot = 1
- iii. However, since some questions are worded differently, they are reverse coded in the following manner:
 - Not at all = 1
 - A Little = 2
 - Quite a Bit = 3
 - A Lot = 4
- iv. The total possible score on the DEMQOL ranges from 28 - 112, with lower scores indicating a lower quality of life. The total possible score on the DEMQOL-Proxy ranges from 30 to 120. If a DEMQOL-Proxy is conducted, the total score is calculated and scaled to fit the same scoring range as the DEMQOL. If DEMQOL-Proxy total score = X , then $(X/30) \times 28$ = DEMQOL (summary/scaled) total score.
- v. The final item on the DEMQOL (and DEMQOL-Proxy), asks how the PWD would rate his/her overall quality of life. This item has the following options and coding:
 - Poor = 1
 - Fair = 2
 - Good = 3
 - Very Good = 4
- vi. This final item is not included in the total score on the DEMQOL (nor on the DEMQOL-Proxy)

5. Geriatric Depression-Short Form (GDS-SF)

- a. A researcher will conduct a direct interview with the PWD to complete the GDS-SF.
- b. The GDS-SF is a 15-item self-reported measure of depression in older adults that is conducted via direct interview.
 - i. Each item on the GDS-SF has two options:
 - YES
 - NO
 - ii. Each YES/NO item is coded with a *one* or *zero* depending on the question's

positive or negative assumed premises, scoring points for responses symptomatic of depression.

1. Scoring example: Item 1

a. *Are you basically satisfied with your life?*

YES = 0

NO = 1

2. Scoring example: Item 4

a. *Do you often get bored?*

YES = 1

NO = 0

iii. The total possible score on the GDS-SF ranges from 0 – 15, with higher scores indicating signs of depression.

6. PEER Leader Assessment

- a. A researcher will conduct the Leader Assessment by interviewing a resident using the assessment form.
- b. The assessment uses various portions of multiple PEER activities to determine the ability of a resident to lead an activity.

7. Neuropsychiatric Inventory-Nursing Home (NPI-NH)

- a. A researcher will conduct the NPI-NH by interviewing a proxy (staff/caregiver) who is familiar with the PWD.
- b. The NPI-NH is a comprehensive assessment of psychopathology in PWD, focused on people residing in nursing homes. The NPI-NH evaluates 12 neuropsychiatric symptoms in dementia patients in the nursing home setting, including the following: Delusions, Hallucinations, Agitation, Depression / Dysphoria, Anxiety, Apathy, Irritability, Euphoria, Disinhibition, Aberrant Motor Behavior, Nighttime Behavior, and Appetite / Eating Changes.
 - i. Each item is initially rated as *present* or *absent*.
 - ii. If the symptom is present, the interviewee is asked to rate the frequency (1 to 4) and severity (1 to 3) of the symptom for the PWD
 - iii. A *frequency x severity* score is then calculated for each item; if a symptom is absent, the frequency x severity score is 0. As such, the total possible score for each of the twelve symptoms ranges from 0 to 12.
- c. A total score is then calculated across all twelve items
 - i. The total possible score on the NPI-NH ranges from 0 to 144.

8. Cohen Mansfield Agitation Inventory (CMAI)

- a. A researcher will conduct the CMAI by interviewing a proxy (staff/caregiver) who is familiar with the PWD.
- b. The CMAI is a scale intended to systematically assess agitation in long-term care residents, including those with dementia. The CMAI consists of 14 items that are posed to a proxy (staff/caregiver) pertaining to the PWD based on observed behaviors over the past two weeks; for example: “During the past two weeks, did the resident display cursing or verbal aggression?” and “Did the resident display constant request for attention for help.”
- c. The frequency of each item is rated on a scale of one (*behavior never occurs*) to five (*behavior occurs a few times an hour or continuous for a half an hour or more*). Therefore, total scores on the CMAI can range from 14 to 70, with higher scores

indicating higher levels of agitation.

9. Observations of PWD in Standard Activities w/ MPES

- a. Researchers will observe PWD's engagement and affect during standard, staff-led activities using the MPES (Camp, Skrajner, & [name], 2015). The MPES is an observational scale that measures four types of engagement: Constructive Engagement: motor/verbal behavior exhibited clearly in response to the target activity; Passive Engagement: listening/watching a target activity; Distracted Engagement: motor/verbal behavior exhibited in response to something other than the target activity; and Non-Engagement / Apathy: outward signs/indicators of apathy, such as sleeping, closing one's eyes, and staring into space. The MPES also measures Pleasure, defined as clearly observable smiling or laughing. Each observation period lasts five minutes, with multiple observations taken on each participant. To ensure MPES data provides a robust comparison for treatment programming, each participant will be observed multiple times, so that averages can be calculated for each type of engagement/affect

Intervention Period Data Collection

1. Treatment Fidelity / Process and Satisfaction Measures

- a. The PWD will be invited to participate in two PEER sessions per week for 4.5 months. For each session, a Session Observation / Evaluation Form will be completed.

Session Observation / Evaluation Form

- i. The following is a full description of the Session Observation / Evaluation Form.
 1. Items that specifically apply to Resident-Leaders (RLs) are preceded with **RL***
 2. Items that specifically apply to Resident-Players are preceded with **RPs***
- ii. During each session, a two-page Session Observation / Evaluation Form will be completed. Since the steps required to lead each activity type differ, distinct Session Observation / Evaluation Forms have been created for each activity type (e.g., there is a Hearthside Book Club Session Observation / Evaluation Form, a Lingo Bingo Session Observation / Evaluation Form, etc.) However, certain parts of the form remain the same for all activities, as described next.
 1. On the top of PAGE 1 of ALL Session Observation / Evaluation Forms, the following data is collected (i.e., these data are consistently collected across all activity types):
 - a. Date of session
 - b. Person filling out form (researcher)
 - c. Site
 - d. # of Leader Form for the Day
 - e. **RL*/RPs*** # of Residents Attended the Activity (for that session)
 - f. Topic (or HBC Story)
 - g. Session Start Time

- h. Session End Time
- i. Length of Session
- j. Staff ID (site staff member)
- k. **RL*** Resident Leader (RL) ID
- l. **RPs*** Resident Player (RP) IDs (all who attended)

2. The remainder of PAGE 1 includes items that are unique to each activity type; these items track...

- a. **RL*** the extent to which the Resident Leader (RL) *completed* each step required to facilitate that particular activity
 - i. For steps that only occur once (e.g., say your name out loud), there are two options: YES and NO.
 - ii. For steps that occur more than once (e.g., ask someone to read the page aloud), there are three options : YES, MORE THAN $\frac{1}{2}$ OF THE TIME; YES, UP TO $\frac{1}{2}$ OF THE TIME; and NO.
- b. **RL*** the amount of staff help needed for that step.
 - i. There are three options: NOT AT ALL, A LITTLE, AND A LOT.
- c. To see the exact steps tracked for each activity, see the forms themselves in the Appendix.

3. On PAGE 2 of ALL Session Observation / Evaluation Forms, the following data is collected (i.e., these data are consistently collected across all activity types):

- a. **RL*** Did the RL use the physical button? (YES / NO / N/A)
- b. **RL*** If NO TO 16, why not?
- c. **RL*** How often did the NEXT button work successfully for the RL, even if he/she had to try more than once? (whether using the on-screen button or physical button) (NOT AT ALL / UP TO $\frac{1}{2}$ / MORE THAN $\frac{1}{2}$ / N/A)
- d. **RL*** How often did RL have to press more than once to get the NEXT button to work? (whether using the on-screen button or physical button) (NOT AT ALL / UP TO $\frac{1}{2}$ / MORE THAN $\frac{1}{2}$ / N/A)
- e. **RL*** How often did the STAFF member press the NEXT button for the RL? (whether using the on-screen button or physical button) (NOT AT ALL / UP TO $\frac{1}{2}$ / MORE THAN $\frac{1}{2}$ / N/A)
- f. **RL*** In the researcher's opinion, did the STAFF member assist the RL more than necessary? (Could the staff member allow the resident-leader more autonomy/independence in leading activity?) (YES / NO / N/A)
- g. **RL*** How often did the RL have difficulty pressing the NEXT button? (whether using the on-screen button or physical button) (NOT AT ALL / UP TO $\frac{1}{2}$ / MORE THAN $\frac{1}{2}$ / N/A)

- h. **RL*/RPs*** Would you do this again sometime? (tally all participants, even if not study)
- i. **RL*/RPs*** Did you like the activity? (tally all participants, even if not study)
- j. **RL*/RPs*** Would you recommend it to others? (tally all participants, even if not study)
- k. **RL*** How often did the RL read a prompt too soon? (NOT AT ALL / UP TO ½ / MORE THAN ½ / N/A)
- l. **RL*** How often did the RL read a prompt too quickly for participants to understand/hear? (NOT AT ALL / UP TO ½ / MORE THAN ½ / N/A)
- m. **RL*** How often did the RL read a prompt unnecessarily? (NOT AT ALL / UP TO ½ / MORE THAN ½ / N/A)
- n. **RL*** How often did the RL press the next button too soon? (NOT AT ALL / UP TO ½ / MORE THAN ½ / N/A)
- o. **RL*** How often did the RL seem quite confused about what to do next? (NOT AT ALL / UP TO ½ / MORE THAN ½ / N/A)
- p. STAFF 1. Did STAFF successfully and appropriately set up the tablets? (YES / NO / N/A)
- q. STAFF 2. Did STAFF have any difficulty using the special table (if applicable)? (YES / NO / N/A)
- r. STAFF 3. Did the STAFF member attach the button to the RL tablet? (YES / NO / N/A)
- s. STAFF 4. Did the STAFF member attach the button to the RP tablets? (YES / NO / N/A)
- t. STAFF 5. Did you enjoy this activity? (YES / NO / N/A)
- u. STAFF 6. Do you think the residents enjoyed it? (YES / NO / N/A)
- v. STAFF 7. Would you do it again sometime? (YES / NO / N/A)
- w. STAFF 8. Would you recommend it to colleagues? (YES / NO / N/A)

2. Observations of PWD in PEER Sessions w/ MPES

- a. Researchers will observe PWD's engagement and affect during PEER sessions using the MPES (Camp, Skrajner, & [name], 2015). The MPES is described above. There are six different types of activities, and each activity type will be used at least six times by each PEER group. Each participant will be observed multiple times during the intervention period, so that averages can be calculated for each type of engagement/affect.

Post-Treatment Assessments

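### The DEMQOL and DEMQOL-Proxy item counts, score ranges and conversion formula cannot all hold under one counting rule, so converted proxy scores may be up to 4 points too high

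*Protocol*

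**What the plan says.** Protocol section 8.0, item 4 of the baseline assessments, sets out the scoring. On length: "The DEMQOL is a 28-item self-reported measure" and "The DEMQOL-Proxy is a 31-item measure completed by the staff/caregiver". On coding: "Each item on the DEMQOL (and DEMQOL-Proxy) has four response-options", worth 1 to 4 points, with some items reversed. On the overall quality-of-life question that closes each form: "This final item is not included in the total score on the DEMQOL (nor on the DEMQOL-Proxy".

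The self-report range is given as follows: "The total possible score on the DEMQOL ranges from 28 - 112, with lower scores indicating a lower quality of life". For the other form: "The total possible score on the DEMQOL-Proxy ranges from 30 to 120". The conversion, meant to bring proxy totals onto the self-report scale, is: "If DEMQOL-Proxy total score = X , then $(X/30) \times 28$ = DEMQOL (summary/scaled) total score".

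The proxy form is used when the resident cannot answer. Sections 8.0 and 10.0 apply that test at baseline and again after treatment, and no rule keeps a resident in the same mode. The SAP names DEMQOL as a distal outcome, tested by a Group x Time interaction.

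**The concern.** With every item coded 1 to 4, a form's range follows directly from its number of scored items. The self-report range needs 28 scored items, equal to the stated count. The proxy range needs 30, one fewer than the stated count. Yet the final item is removed from both totals, so the two counts appear to treat it differently, and the text does not say so.

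This matters because the divisor and multiplier of an operative scoring formula come from these counts. If either is wrong by one, proxy scores sit on a slightly different scale from self-report scores. A resident who answers for himself or herself at one visit and is rated by proxy at the other would then show a change produced by the formula alone. Proxy use is plausible: section 6.1 admits residents scoring below 5 on the MMSE if they score at least 1 on the skills inventory.

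**Working it through.** **Inputs** (all from Protocol section 8.0, item 4): 28 DEMQOL items; 31 DEMQOL-Proxy items; codes 1 to 4; final item excluded from both totals; ranges 28–112 and 30–120; conversion X × 28/30.

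**Step 1. Reproduce the plan's conversion.** 30 × 28/30 = 28 and 120 × 28/30 = 112. The formula therefore agrees with the two stated ranges. Together they imply 28 scored self-report items and 30 scored proxy items.

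**Step 2. Derive the ranges from the item counts.** With k scored items the range is k to 4k.

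| Do the stated counts include the final item? | DEMQOL range | Proxy range | Correct factor | Fits both stated ranges? |
|---|---|---|---|---|
| A. Neither count does | 28–112 | 31–124 | 28/31 | No, proxy differs |
| B. Both counts do | 27–108 | 30–120 | 27/30 | No, DEMQOL differs |
| C. Only the 31 does | 28–112 | 30–120 | 28/30 | Yes, but by two different rules |

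The fourth combination (only the 28 includes it) gives 27–108 and 31–124, which fits neither range, and is not pursued.

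**Step 3. Size of the error.** The comparison holds the mean item score equal on the two forms.

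- A: excess = X × 28/30 − X × 28/31; ratio 31/30 = 1.033.
- B: excess = X × 28/30 − X × 27/30 = X/30; ratio 28/27 = 1.037.
- C: excess = 0.

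| Mean item score | A: X | A: stated v correct | A: excess | B: X | B: stated v correct | B: excess |
|---|---|---|---|---|---|---|
| 1 | 31 | 28.93 v 28.0 | 0.93 | 30 | 28.0 v 27.0 | 1.0 |
| 2 | 62 | 57.87 v 56.0 | 1.87 | 60 | 56.0 v 54.0 | 2.0 |
| 2.5 (mid-scale) | 77.5 | 72.33 v 70.0 | 2.33 | 75 | 70.0 v 67.5 | 2.5 |
| 3 | 93 | 86.80 v 84.0 | 2.80 | 90 | 84.0 v 81.0 | 3.0 |
| 3.5 | 108.5 | 101.27 v 98.0 | 3.27 | 105 | 98.0 v 94.5 | 3.5 |
| 4 | 124 | 115.73 v 112.0 | 3.73 | 120 | 112.0 v 108.0 | 4.0 |

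Under A the top converted score, 115.7, exceeds the DEMQOL maximum of 112. Under B the top converted score, 112, exceeds 108.

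**Step 4. Effect on the change score.**

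- Self-report at one visit and proxy at the other: the whole excess enters the change, upward if proxy comes second and downward if it comes first.
- Proxy at both visits: the change is stretched by 3.3% (A) or 3.7% (B).
- Between arms: false difference = (net difference between arms in the share switching to proxy) × excess. The documents give no such share. For an assumed net difference of 0 to 20% and a mean item score of 3, it runs from 0 to 0.20 × 2.8 = 0.56 points (A) or 0.20 × 3.0 = 0.60 points (B).

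**Step 5. Effect on data checks.** Section 16.2 calls for a check on out-of-range values. Under A, the stated proxy range would flag valid totals of 121 to 124 and accept a total of 30, which a complete form cannot produce.

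**The case against.** The strongest reply is that the scoring figures agree among themselves. The proxy minimum, maximum and divisor all point to 30 scored items, and 31 less the excluded final item is 30. On that view the count of 31 includes the overall question, the count of 28 does not, and the defect is loose description with no scoring error. No text requires the two counts to follow the same rule, and the forms, which the protocol places in its Appendix, are not in the text available here. This reply stands as far as it goes: row C cannot be excluded, and under it the formula is right.

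It does not remove the point. Row C needs two adjacent counts to be made by different rules without a word to say so, and the two rows that use one rule both make the formula too high.

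It is also fair to say that similar switching in the two arms would largely cancel in the Group x Time test, and that whether self-report and proxy ratings should be combined at all is a larger question. Both are true. The second is separate from the arithmetic.

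**Conclusion.** The inconsistency is certain; the size of any scoring error is conditional. The stated formula is too high by 3.3% (0.9 to 3.7 points) if neither count includes the final item, by 3.7% (1.0 to 4.0 points) if both do, and by nothing if only the proxy count does.

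A reader might infer that proxy scores definitely land about 3 points too high. The documents do not support that. The error may be zero, and where it exists it is proportional to the score: 2.3 to 2.5 points at mid-scale, and close to 3 only for mean item scores around 3 to 3.5. A reader might also infer a bias between arms. That needs unequal switching of mode, for which the documents give no evidence; the 0 to 0.6 points shown rests on an assumed share. With no proxy share, DEMQOL standard deviation or effect size stated, the effect on the Group x Time test cannot be computed.

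The point still deserves correction before analysis. It concerns the scoring of a named SAP outcome, and the mode of collection is decided afresh at each visit.

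**What to change.** 1. Count the scored items on the two forms actually in use, leaving out the final overall item on each.
2. Define scaled score = (number of scored DEMQOL items) × (Proxy total ÷ number of scored Proxy items). The factor is 28/31 if 28 and 31 items are scored, 27/30 if 27 and 30 are, and stays 28/30 if 28 and 30 are.
3. Correct the item counts and ranges in section 8.0 to match, saying for each form whether the count includes the final item.
4. Recompute any scores already converted from the raw proxy totals.
5. Add a check that no scaled score exceeds the DEMQOL maximum, and record the mode of interview at each visit so that switches can be identified.

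The cost is a few lines in the protocol and the scoring syntax. No new data are needed beyond the raw totals and a note of mode. If the forms prove to have 28 and 30 scored items, only the wording changes.
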